## 12.7. Withdrawal Due to Adverse Events

Withdrawal due to AE should be distinguished from withdrawal due to insufficient response, and recorded on the appropriate CRF. When a subject withdraws due to an SAE, the SAE must be reported in accordance with the reporting requirements (see Section 12.9).

## 12.8. Eliciting Adverse Event Information and Reporting

The investigator is to report all directly observed AEs and all AEs spontaneously reported by the study subject. Each study subject will be questioned about AEs. Each AE is to be assessed to determine if it meets the criteria for SAEs. If an SAE occurs, expedited reporting will follow the provisions of Section 12.9.

## 12.9. Serious Adverse Event Reporting Requirements

If an SAE occurs, Xeris Pharmaceuticals is to be notified within 24 hours of awareness of the event by the investigator. In particular, if the SAE is fatal or life-threatening, notification to Xeris Pharmaceuticals must be made immediately, irrespective of the extent of available AE information. This time frame also applies to follow-up on previously forwarded SAE reports.

In the rare event that the investigator does not become aware of the occurrence of an SAE immediately (e.g., a study subject initially seeks treatment elsewhere), the investigator is to report the event within 24 hours after learning of the event and document the time of first awareness of the AE.

A death occurring during the study, during the per-protocol follow-up period, or within 30 days after stopping treatment with test drug must be reported to Xeris Pharmaceuticals or its designee(s) immediately, whether or not it is considered treatment-related. Initial SAE reports must be followed by detailed descriptions. These should include copies of hospital case records and other documents when requested. Telephone and e-mail reports must be confirmed promptly either by facsimile or by overnight courier or mail.

### **12.10. Non-Serious Adverse Event Reporting Requirements**

All AEs will be reported on the AE page(s) of the CRF. AEs should be reported using concise medical terminology on the CRFs as well as on the form for collection of the SAE information.

### **12.11. AE Reporting Requirements to Regulatory Authorities**

AE reporting by the Sponsor, including suspected serious unexpected adverse reactions, will be carried out in accordance with applicable regulations.

The investigator must notify the IRB of the occurrence of any SAE, in writing, as soon as is practicable and in accordance with local regulations. A copy of this notification must be provided to Xeris Pharmaceuticals or its designee.

In the event of an SAE that meets the criteria for expedited reporting, an SAE report will be prepared for submission to the FDA and any other applicable authorities by the Sponsor or its designee.

### **12.12. Pregnancy**

The active pharmaceutical product in Xeris Pharmaceuticals' G-Pen™ (glucagon injection) is Glucagon, which is in Pregnancy Category B. Female subjects able to become pregnant will be tested (rapid, urine) for pregnancy at the Screening visit. Any subject found to be pregnant at the Screening visit (Visit 1) will not be randomized to treatment. At both treatment visits and at the follow-up visit (i.e., Visits 2, 3 and 4), pregnancy testing will be repeated. Any subject who is found to be pregnant at one of the treatment visits will be withdrawn from the study immediately and no further study treatments will be given. Pregnancy at the follow-up visit will be noted, but the visit will be completed. Any pregnancy in a subject who received at least one dose of study drug will be followed until resolution (i.e., birth or voluntary or spontaneous termination of the pregnancy). Any pregnancy outcome that meets the criteria for an SAE will be reported as an SAE.

### **12.13. Subject Monitoring**

Subjects will be monitored for AEs throughout the study by the study unit staff. The principal investigator or designated sub-investigator will be on site for drug administration and until 4 hours after administration of study drug to the last subject. The principal investigator or designated sub-investigator will also be on call for the remainder of the treatment visit. If necessary, a physician, either at the study site or in a nearby hospital, will administer treatment for any AEs.

Safety parameters, including laboratory results and ECGs, will be assessed by the principal investigator or his delegate using the site's criteria for clinical laboratory and ECG acceptance ranges as suggested guidelines in making the medical assessment.

Scheduled safety measurements will be repeated according to appropriate SOPs or upon request from a physician. Any abnormal repeated measurement will be evaluated by a physician and repeated if judged necessary. Further action may be taken on the physician's request.

Subjects will be advised to notify their health care professionals (e.g., physician, dentist, and/or pharmacist) that they are participating in a clinical research study of a drug called synthetic Glucagon Injection before taking any medicines or undergoing any medical procedure.

## 13. DATA ANALYSIS AND STATISTICAL METHODS

### 13.1. Efficacy

The primary objective is to verify that the G-Pen is non-inferior to control in terms of hypoglycemia relief. The primary comparison will be performed using the intent-to treat (ITT) cohort defined as all subjects randomized to one of the two sequence groups: G-Pen followed by control, or control followed by G-Pen. A failure for either treatment will be recorded if plasma glucose remains  $\leq 70.0$  mg/dL throughout the 0-30 minute period from the drug administration. Consistent with ICH Guideline E9, excluded from the ITT analysis will be subjects who fail to meet all eligibility criteria and/or are randomized to treatment, but receive neither study drug.

The following scoring system will be applied to all subjects in the ITT cohort. If a G-Pen failure is observed then the treatment failure score = 1; similarly the control failure score = 1 if a control failure is observed. If the G-Pen treatment outcome is missing then the treatment failure score = 0.2. A missing control outcome yields a control failure score = 0.1. An observed successful plasma glucose rising above 70.0 mg/dL within 30 minutes yields a failure score = 0, for either treatment. Therefore, all subjects in the ITT cohort will have G-Pen and control failure scores [Koch].

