#### 13.1.1. Primary Endpoint:

The G-pen acceptance criterion will be based on the sample mean of the treatment minus control failure scores from each subject in the ITT population. If  $D_{ht}$  is the sample mean of the G-Pen minus control failure difference, and SE is the estimated standard error of  $D_{ht}$  (square root of the estimated G-Pen minus control variance divided by the sample size), then the G-Pen will be accepted provided:

$$D_{ht} + 2.6 SE \leq 0.1.$$

This criterion, particularly the value 2.6, came from Monte-Carlo simulations from selected scenarios where the population G-Pen failure rate exceeded the control rate by 0.1. Under these circumstances the rate of G-Pen acceptance was found to be within 0.025 using this criterion, with missing data rates within 15%. This bound of 0.025 on the type 1 error rate was observed for control failure rates up to 5%. Monte Carlo simulation rather than asymptotic normality is necessary because an observed failure from either G-Pen or control is expected to be low, less than 5%.

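### The 0.2/0.1 scores for missing outcomes favour G-Pen when control outcomes are missing more often, a case in which the stated 0.025 bound can fail; at n = 75 with few control-only failures it fails even with complete data

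*Combined protocol and SAP*

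**What the plan says.** Section 13.1, repeated in the Synopsis, gives every subject in the ITT cohort a failure score for each product: 1 for an observed failure, 0 for an observed success. For missing outcomes: "If the G-Pen treatment outcome is missing then the treatment failure score = 0.2" and "A missing control outcome yields a control failure score = 0.1". Subjects who received neither drug are excluded.

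Section 13.1.1 accepts G-Pen if the mean G-Pen-minus-control score plus 2.6 standard errors is at most 0.1. The rule, "particularly the value 2.6, came from Monte-Carlo simulations from selected scenarios" in which "the population G-Pen failure rate exceeded the control rate by 0.1". On type 1 error it states that "the rate of G-Pen acceptance was found to be within 0.025 using this criterion, with missing data rates within 15" per cent, and "This bound of 0.025 on the type 1 error rate was observed for control failure rates up to 5" per cent. It also says that "an observed failure from either G-Pen or control is expected to be low, less than 5" per cent.

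Section 13.1.2 describes the simulation: 75 draws from a 3x3 table, with missingness independent of outcome. Its 1% limit on discordant cells is attached to the power runs. No discordant cells are given for the type 1 error runs, and no split of missing data between products is given for either.

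**The concern.** A missing control outcome is scored at no less than twice the failure rate the plan expects. A subject with a G-Pen success and a missing control scores 0 - 0.1 = -0.1, which is better for G-Pen than two observed successes (score 0). If control outcomes go missing more often than G-Pen outcomes, the mean difference moves towards acceptance. In a non-inferiority trial that is the direction that matters, and the single figure quoted for type 1 error does not show whether such cases were examined.

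**Working it through.** **Inputs.** Scores 0.2/0.1, multiplier 2.6, margin 0.1, control failure up to 5% and missing up to 15% (Sections 13.1 to 13.1.2). n = 75 is the planned evaluable number and n = 80 the approximate number randomized (Section 9.1). Notation: pG and pC are the failure rates, mG and mC the missing rates, and p01 the probability of control failure with G-Pen success. *Assumed, because not given:* p01 from 0 to 5% under the null, and several missing splits. Simulations follow the plan's 3x3 model with 200,000 to 400,000 replicates and cover only the score rule, not the Synopsis's additional count rule.

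**1. Mean difference at the margin (pG = pC + 0.1).**

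E[D] = (1 - mG)pG + 0.2mG - (1 - mC)pC - 0.1mC

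= 0.1 + mG(0.2 - pG) - mC(0.1 - pC)

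= 0.1 + (mG - mC)(0.1 - pC), because 0.2 - pG = 0.1 - pC.

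- Equal missingness: exactly 0.1, so no bias.
- 15% missing on control only, pC = 1%: 0.1 - 0.15 x 0.09 = 0.0865.
- The same with scores 0.15/0.05: 0.1 - 0.15 x (0.05 - 0.01) = 0.094.

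**2. The plan's own figures.** Power reproduces: the worst balanced case stated (5% failures, discordant cells 1%, 15% missing on each product, n = 75) gives 90.8%.

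The type 1 error bound reproduces only in part, even with no missing data. With p01 = 0 and n = 75:

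- 3 G-Pen failures: 0.0400 + 2.6 x sqrt(0.04 x 0.96/74) = 0.0992, accepted.
- 4 failures: 0.1212, rejected.
- Type 1 error = P(Bin(75, 0.1) <= 3) = 0.050.

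At n = 80 the cut-off is again 3 failures (0.0931 accepted, 0.1138 for 4), so P(Bin(80, 0.1) <= 3) = 0.035. At n = 75 simulation gives 0.029 for p01 = 1%, 0.023 for 1.5% and 0.018 for 2%. No missing-data score enters any of these.

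**3. Type 1 error with 15% missing on control only.**

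| n | pC | p01 | complete data | scores 0.2/0.1 | scores 0.15/0.05 |
|---|---|---|---|---|---|
| 80 | 1% | 1% | 0.021 | 0.044 | 0.026 |
| 80 | 3% | 1% | 0.021 | 0.038 | 0.021 |
| 75 | 2% | 2% | 0.018 | 0.030 | 0.021 |
| 75 | 1% | 1% | 0.029 | 0.040 | 0.030 |
| 75 | 0 | 0 | 0.050 | 0.054 | 0.051 |

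In the first three rows complete data meet 0.025 and the current scores break it. In the last two the breach is already there. With p01 of 3% or 5% the same split gives 0.023 or 0.014 at n = 75; at n = 80 these cases also stay below 0.025.

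**4. Milder or balanced splits (pC = p01 = 1%).**

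- 6% missing on control only: 0.030 at n = 75 (0.029 complete) and 0.024 at n = 80.
- 15% missing on each product, n = 75: 0.022 with current scores and 0.024 with 0.15/0.05.

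**5. Power at equal failure rates, discordant cells 1%, n = 75.**

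| 15% missing on | total failures | 0.2/0.1 | 0.15/0.05 |
|---|---|---|---|
| G-Pen only | 1% | 88.2% | 93.9% |
| each product | 5% | 90.8% | 91.7% |
| control only | 5% | 97.8% | 96.8% |

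The first row is below the plan's stated 90%. At n = 80 the control-only figure goes from 98.7% to 96.8%.

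**The case against.** The two scores form a pair, and the 0.1 gap between them equals the margin. Under balanced loss the pair is unbiased at the margin, and at n = 75 with p01 = 1% it lowers type 1 error from 0.029 to 0.022. When only G-Pen outcomes are missing it is conservative. Sequence is randomized 1:1, so loss after the first visit should fall on both products. The plan allows for about 5/80 = 6% loss. A 15%/0% split arising from drop-out after the first visit would need about 30% of the G-Pen-first sequence to leave and nobody from the other. The type 1 error runs may also have used larger discordant cells, for which the bound holds. All of this stands, and it limits the point to control-heavy missingness with few control-only failures.

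A reader might infer three stronger things that the documents do not support:

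- *That the missing-data score is what breaks the bound generally.* At n = 75 with p01 of 1% or less, the breach is present with complete data.
- *That poor tolerance of G-Pen would drive control outcomes to be missing.* Nothing in the plan says so, and its simulation model takes missingness as independent of outcome.
- *That rescoring alone restores 0.025.* It leaves 0.026 and 0.030 in two of the rows above and does nothing for p01 = 0.

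What the objection does not answer is that the bound is stated for missing rates within 15% with no condition on how they split.

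**Conclusion.** The concern holds in a limited form. The 0.2/0.1 pair favours G-Pen only when control outcomes are missing more often than G-Pen outcomes, by (mC - mG)(0.1 - pC) in the mean. At 15% control-only missing this is enough to break the stated bound in scenarios that meet it with complete data: 0.021 to 0.044 (n = 80, pC and p01 both 1%) and 0.018 to 0.030 (n = 75, both 2%). These figures rest on an extreme assumed split and on assumed discordant cells. At the plan's expected loss of about 6%, all on control, n = 80 gives 0.024, inside the bound.

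The failure with complete data at n = 75 (0.029 at p01 = 1%, 0.050 at p01 = 0) is a separate matter and belongs to the multiplier. As stated, the 0.025 bound is not supported over the whole range claimed for it.

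**What to change.** 1. In Section 13.1 and the Synopsis, score a missing control outcome 0.05, the top of the plan's own expected range, and a missing G-Pen outcome 0.15. This keeps the 0.1 gap, and so the absence of bias under balanced missingness.
2. Rerun the 3x3 simulation at n = 75 and n = 80 with one-sided as well as balanced missingness and control-only failures from 0 to 5%. Report the grid in Sections 13.1.1 and 13.1.2.
3. Either re-derive the multiplier or restate the 0.025 bound with the range in which it holds. As a guide, with complete data at n = 75 a multiplier of 2.7 gives about 0.016 at p01 = 0 and 0.020 at p01 = 1%; its effect on power was not examined here.

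The cost is wording and a rerun of an existing simulation, with no extra subjects and no change to endpoint or margin. There are two downsides. Power falls by about 1 to 2 points when only control outcomes are missing. When only G-Pen outcomes are missing (15%, p01 = 1%), the rule becomes less conservative: type 1 error rises from about 0.009-0.012 to 0.016-0.020, still under 0.025.

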Following dosing, plasma glucose will be monitored every 5 minutes until 90 minutes post-dosing. Additional blood samples will be collected at -5, 0, 10, 20, 30, 45, 60, 90, 120, 180 and 240 minutes and stored at -70C for determination of plasma glucagon and potentially insulin levels. After this, the subject will resume insulin pump therapy, if applicable, and will be given a meal. The subject can then leave the clinic after glucose concentration is confirmed to be between 70 and 180 mg/dL.

Subjects will complete a questionnaire regarding hypoglycemia symptoms at the start of the hypoglycemia induction period and periodically until 30 minutes post-treatment with glucagon. The hypoglycemia induction procedure is expected to elicit symptoms of a hypoglycemic response. However, the procedure is not expected to be of sufficient duration, or to generate such a low glucose concentration in the CNS that it will impair consciousness characteristic of severe hypoglycemia.

After a wash-out period of 7 to 28 days, subjects will return to the clinic and the study procedures will be repeated with each subject crossed over to the other treatment. After study-related procedures are performed on each of the treatment days, subjects will be discharged. A follow-up visit will be conducted 3-14 days following administration of the final dose as a safety check.

Tolerability will be assessed by comparing adverse event reports between the groups. In addition, subjects will complete questionnaires concerning injection site discomfort. An investigator will use modified Draize scales to evaluate the injection sites following each administration.

Data management and statistical analysis:

Data will be entered into an electronic Case Report Form by site personnel. Data will be monitored at on-site visits by Xeris personnel or by a CRO acting as Xeris' agent.

The primary comparison will be performed using the intent-to treat (ITT) cohort defined as all subjects randomized to one of the two sequence groups: G-Pen followed by control, or control followed by G-Pen. A failure is recorded if the subject's plasma glucose fails to rise above 70.0 mg/dL within 30 minutes of the start of therapy.

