### 5.3. Endpoints

#### 5.3.1. Primary Endpoint

Treatment success in this study will be based on a primary endpoint of an increase in plasma glucose concentration from below 50.0 mg/dL to greater than 70.0 mg/dL within 30 minutes after receiving glucagon.

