Note: If consecutive readings of plasma glucose < 50.0 mg/dL are not achieved within 3 hours of the start of the hypoglycemia induction phase, the visit should be terminated. In this case:

- i. Study drug should NOT be given.
- ii. The visit should be terminated and rescheduled after a 7-day minimum wash-out period.
- iii. If appropriate, insulin pump therapy should be restarted and a meal provided. The subject can leave the clinic after plasma glucose is confirmed to be between 70 and 180 mg/dL.
- h. Following study drug administration, plasma glucose will be measured every  $5 \pm 2$  minutes until 90 minutes post-dosing. Note: At their discretion, investigators may continue to monitor glucose levels for safety during the remainder of the visit.
  - i. At any time post-dosing if a subject exhibits signs of coma or convulsions, or if plasma glucose remains < 60.0 mg/dL at 30 minutes post-dosing, a 25 mL IV bolus dose of 50% dextrose will be given. Signs and symptoms should be monitored and if the subject's condition fails to improve within 15 minutes, additional dextrose or other intervention may be given at the discretion of the investigator.
  - j. Additional blood samples will be collected at 10, 20, 30, 45, 60, 90, 120, 180 and 240 minutes post-dosing with  $\pm$  5 minutes per collection, and processed and stored at -70C for determination of plasma glucagon and potentially insulin levels (see Table 5).
  - k. At 240 minutes post-dosing, the subject will resume pump therapy, if applicable, and will be given a meal. The subject can then leave the clinic after plasma glucose is confirmed to be between 70 and 180 mg/dL. Note: If necessitated by rising glucose levels, insulin pump therapy can be re-started as early as 120 minutes post-dosing. Additionally, IV insulin can be administered to non-pump using subjects to prevent hyperglycemia, starting at 120 minutes post-dosing with glucagon.

8. Subjects will complete a questionnaire regarding severity of hypoglycemia symptoms ([Appendix 1](#)) at various time points, including:
  - a. Just before the IV bolus push dose of insulin is given at the start of the hypoglycemia induction procedure.
  - b. Every time blood is drawn for evaluation of plasma glucose concentration during the induction procedure.
  - c. Just before study drug is administered, and

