#### 13.1.2. Sample Size Calculation:

Using the above criterion, a sample size of 75 subjects yields probabilities of G-Pen acceptance of over 90% if the population failure rates of G-Pen and control are equal, and the rate of missing observations is within 15%. These results were obtained using Monte Carlo simulations with G-Pen and control total failure rates up to 5%, and with G-Pen success Control failure, or G-Pen failure Control success within 1%.

The power and type 1 error bounds were obtained from a simulation model using a 3x3 table of outcomes for G-Pen and control. The three outcomes for each were Success, Failure, and Missing. Probabilities were assigned to each of the 9 cells, with the missing outcome being

stochastically independent of the Success, Failure outcome combinations. Also the failure score difference, G-Pen minus control, was assigned to each of the nine cells. To simulate one replicate of the study, 75 independent draws were made from the multinomial distribution determined by the probabilities from the 9 cells, and the sample mean, estimated standard error were computed. The G-pen acceptance criterion was applied and either a 0 (G-pen failed) or 1 (G-pen accepted) was recorded. This was repeated 10,000 times to obtain the estimated probability of G-pen acceptance under the conditions defined by the cell probabilities. The simulations were performed using R version 3.1.2 (2014-10-31).

Approximately 80 subjects will be randomized at approximately 8 clinical sites with a goal of no single center accounting for > 20% of the total randomization.

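### As the protocol is written, a glucose value that first passes 70.0 mg/dL after IV dextrose inside the 30-minute window counts as a glucagon success (rare case, low severity)

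*Combined protocol and SAP*

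**What the plan says.** Section 5.3.1 defines success as a rise in plasma glucose from below 50.0 mg/dL "to greater than 70.0 mg/dL within 30 minutes after receiving glucagon". Section 13.1 records a failure only if glucose stays at or below 70.0 mg/dL "throughout the 0-30 minute period from the drug administration", and then scores the outcome: "An observed successful plasma glucose rising above 70.0 mg/dL within 30 minutes yields a failure score = 0, for either treatment". A failure scores 1. A missing outcome scores 0.2 for G-Pen and 0.1 for control. The synopsis and Section 5.1 use the same glucose-only definition. None of these places mentions rescue.

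Section 10.2.1, item 7, has two triggers for IV dextrose. One has no time limit: "At any time post-dosing if a subject exhibits signs of coma or convulsions". The other is a glucose still below 60.0 mg/dL at 30 minutes. The same item keeps sampling going: "Following study drug administration, plasma glucose will be measured every" 5 ± 2 minutes, up to 90 minutes.

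Section 13.1.1 accepts G-Pen if Dht + 2.6 SE is at most 0.1, with SE given as the "square root of the estimated G-Pen minus control variance divided by the sample size". The synopsis adds a count criterion: G-Pen minus control failures not above 3, and G-Pen failures not above 4, once the 75th evaluable subject has completed both periods. Section 13.5 leaves further detail on Sections 13.1 to 13.5 to a SAP.

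**The concern.** The primary objective in Section 5.1 is the efficacy of the glucagon product. A reading that first exceeds 70.0 mg/dL after intravenous glucose does not show that the product worked. Yet the reading is observed, so the missing-outcome scores do not apply, and it falls inside the window, so the failure definition is not met. The stated rule gives it a score of 0.

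This matters because the verdict rests on a handful of failures in about 75 subjects, so a single score can decide it. The protocol takes care to assign scores to missing outcomes but does not say whether readings after rescue are meant to count. If a case arose, that choice would have to be defended after the event.

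**Working it through.** **1. Which subjects are affected.** All of the following must hold: dextrose is given before 30 minutes; no earlier reading exceeded 70.0 mg/dL; a later reading inside the window does.

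- Before 30 minutes the only trigger is signs of coma or convulsions.
- Dextrose given on the 30-minute glucose trigger comes when failure is already on record, unless an earlier reading had passed 70.0 mg/dL.
- A rescued subject who stays at or below 70.0 mg/dL remains a failure.

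**2. Check of the plan's own figure.** Section 13.1.2 states power above 90% with 75 subjects, equal failure rates up to 5%, each discordant cell within 1%, and missing data within 15%. Simulating its 3 × 3 table (100,000 replicates, missingness taken as independent between treatments) gives 0.909 at the upper limits of all three inputs. The stated power reproduces, so the rule below is applied as the protocol intends.

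**3. The Section 13.1.1 rule at the boundary.** With no missing data, let S be the sum of the subject differences (G-Pen score minus control score) and Q the sum of their squares. Then Dht = S/n, variance = (Q − n·Dht²)/(n − 1), and SE = √(variance/n).

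For n = 75:

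- Three G-Pen-only failures: Dht = 3/75 = 0.0400; variance = (3 − 0.12)/74 = 0.0389; SE = 0.0228; 0.0400 + 2.6 × 0.0228 = 0.0992, accept.
- Four G-Pen-only failures: Dht = 4/75 = 0.0533; variance = (4 − 0.2133)/74 = 0.0512; SE = 0.0261; 0.0533 + 2.6 × 0.0261 = 0.1212, reject.
- Four G-Pen-only and one control-only: Dht = 0.0400; variance = (5 − 0.12)/74 = 0.0659; SE = 0.0297; result 0.1171, reject.

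At n = 80 the boundary is the same: 0.0931 for three G-Pen-only failures and 0.1138 for four.

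**4. Effect of rescoring, under both stated criteria** (n = 75, no missing data). The first column scores the rescued session as a failure. The second shows what the protocol text would record.

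| Rescue scored 1 | As recorded | Section 13.1.1 | Synopsis counts |
|---|---|---|---|
| 4 G-Pen-only | 3 G-Pen-only | 0.1212 reject → 0.0992 accept | difference 4, fail → difference 3, pass |
| 3 G-Pen-only plus 1 failing on both; that control failure rescored | 4 G-Pen-only | 0.0992 accept → 0.1212 reject | difference 3, G-Pen 4, pass → difference 4, fail |
| 4 G-Pen-only and 1 control-only; one rescored on each product | 3 G-Pen-only | 0.1171 reject → 0.0992 accept | difference 3, G-Pen 4, pass → pass |
| 5 failing on both; one G-Pen failure rescored | 4 on both, 1 control-only | 0 accept → −0.0133 + 2.6 × 0.0133 = 0.0213 accept | G-Pen 5, fail → G-Pen 4, pass |

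The first two rows show a reversal in each direction under both criteria. The third is a reversal only under Section 13.1.1, the fourth only under the counts.

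**5. If the event also stops dosing.** A convulsion may be an SAE (Section 12.4), and Section 7.3 pauses dosing for an SAE. Suppose it occurs on G-Pen in period 1 and leaves control missing, with three other G-Pen-only failures. The subject's difference is then 0 − 0.1 = −0.1 as recorded, or 1 − 0.1 = 0.9 if scored as a failure. Section 13.1.1 gives 0.0981 (accept) or 0.1183 (reject).

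**6. Why no reversal probability is given.** It would need the share of failures that are rescued early and then read above 70.0 mg/dL, which the documents do not supply. At 5% failure, 75 × 2 = 150 sessions give 7.5 expected failures. Assumed shares of 5%, 10% and 20% imply 0.375, 0.75 and 1.5 such cases per trial. The upper values sit badly with an event that the protocol does not expect.

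**The case against.** The strongest reply is that the case will hardly ever occur. The synopsis says that "the procedure is not expected to be of sufficient duration" to impair consciousness, Section 7.1 repeats that expectation, and Section 8.2 excludes current seizure disorder. This stands, and it sets the severity. It does not close the gap, because Section 10.2.1 itself provides for coma and convulsions.

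Second, handling of rescue is ordinary SAP detail, and Section 13.5 defers to a SAP. This also stands. A reader might infer that the trial has no rule for rescued subjects at all. The documents do not support that, since the SAP was not available. What can be said is that the protocol text, read alone, gives a score of 0.

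Third, counting every reading regardless of rescue is an objective rule, the same for both products, and scoring 1 would blame the glucagon for a convulsion with another cause. That is a defensible position, but the protocol does not say that it takes it, and it fits poorly with an objective about the product's efficacy. The cost of scoring 1 is real and is accepted in the fix.

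Fourth, a reader might infer that rescued subjects in general pass as successes. They do not: step 1 of the working leaves only one narrow group.

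**Conclusion.** The point holds for the protocol text and is minor. The stated rule gives a determinate but wrong score in one narrow situation, on either product. Its practical weight lies at the decision boundary, where one session separates 0.0992 from 0.1212 (75 subjects, no missing data, no control failures), and 3 versus 0 from 4 versus 0 under the synopsis counts.

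A reader might infer that the gap favours G-Pen. The documents do not support a fixed direction: rescoring a G-Pen failure can help G-Pen, and rescoring the control failure of a subject who failed on both can hurt it. A reader might also infer that equal rescues cancel out, or that they never do. That depends on which stated criterion is applied, and the example of four versus one is a reversal only under Section 13.1.1. Nor do the documents support a claim that the trial's conclusion is likely to be affected, since they give no rescue rate.

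**What to change.** State in Sections 5.3.1 and 13.1, and carry into the SAP before unblinding:

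- A subject given IV dextrose, including any follow-up glucose-raising intervention under Section 10.2.1, within 30 minutes of study drug and before any reading above 70.0 mg/dL is scored 1 for that treatment.
- Readings after rescue are not used for the primary endpoint.

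Record the time of rescue in the CRF and report the number of such cases by treatment. If any occur, add a sensitivity analysis that scores them as missing (0.2 for G-Pen, 0.1 for control). With three other G-Pen-only failures and the rescued subject's control a success, that scoring gives 0.1021 at n = 75 and 0.0958 at n = 80, so it is informative at the boundary.

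The cost is one scoring rule, one time field and a conditional analysis. Such an event would probably be documented as an SAE anyway, but no section names a field for the time of dextrose. The downside is a less favourable score in rare cases, including an early convulsion with another cause. Only the scoring changes; the clinical rescue rule stays as it is.
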